## 2.2. Study Products

# 2.2.1 Marathon® XL No Sting Cyanoacrylate Skin Protectant (referred to as Marathon®)

Marathon® (#MSC093001XL) is a non-cytotoxic, fast drying liquid barrier film for the protection of damaged or intact skin from the effects of moisture such as urine, feces, digestive juices,

Medline Industries, LP
An evaluation of the skin protection characteristics of two commercially available skin barrier protectants
MED-2022-DIV71-003
08-AUG-2022

Version 2.0 CONFIDENTIAL Page 11 of 28

perspiration, and wound drainage. It can be used in areas that are exposed to friction (rubbing) or shear (tearing) from bedding, clothing, shoes, or any material that would rub against the skin. It helps protect skin against irritation caused by adhesive products. Marathon® is applied as a liquid and dries within a minute, adhering to the contours of the skin to form a transparent flexible film. It will wear off naturally, as the skin regenerates. The applicator and packaging are sterilized.

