## 2.2.2 3MTM CavilonTM Advanced Skin Protectant (referred to as CavilonTM)

CavilonTM (#MMM5050CS) is a polymeric-cyanoacrylate solution intended for the protection of intact or damaged skin. It is effective in conditions where skin is exposed to moisture and caustic irritants such as feces, digestive fluids, wound drainage and urine, frequently or continuously. It can also be used in areas exposed to friction and shear from bedding, clothing, shoes or any other material that would rub against the skin. Upon application to skin, the liquid dries rapidly to form a primary long-lasting waterproof, highly durable film barrier. It is elastomeric, adhering to the contours of the skin and providing a uniform film. The film is transparent and possesses good oxygen and moisture vapor permeability. The polymer-cyanoacrylate is dispersed in a non-stinging solvent. The film is colorless, non-cytotoxic and has a low dermatitis potential. The film adheres to dry, moist or wet skin surfaces and remains intact during conditions of continuous or repeated exposure to moisture or caustic irritants. It will wear off the skin and does not require removal.

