### 5.3. Strategies for Recruitment and Retention

Participants will be recruited from an internal database of Medline employees who have previously participated in studies conducted by Medline, and/or have agreed to be contacted for future studies, as well as via advertisement(s). Potential participants will be screened and enrolled until a total of 42 participants with complete data are obtained.

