#### 8.2. Randomization

This is a single-blind study, with participants blinded to the SBPs that are applied to them. Due to the primary focus on durability of the SBPs, randomization will target dominant versus non-dominant arms, not left versus right. Participants will be randomized to either Marathon® or CavilonTM, and this SBP will be applied to their dominant arm, as defined by the participant. This ensures an equal probability of Marathon® and CavilonTM on both dominant and non-dominant arms. If a participant has incomplete data, the participant will be replaced such that the randomization sequence of the replaced participant will be assigned to the new participant.

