### 8.3. Populations for Analyses

The analyses will be performed on the intent to treat (ITT) population which consists of all participants who have complete data for all time points and have completed the survey for the secondary endpoint.

No per protocol, safety, or other analyses groups are planned.

Medline Industries, LP
An evaluation of the skin protection characteristics of two commercially available skin barrier protectants
MED-2022-DIV71-003
08-AUG-2022

Version 2.0 CONFIDENTIAL Page 22 of 28

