# Analysis of Secondary Endpoint

### 8.8.2. Secondary Endpoint

The secondary objective of this study is to assess the participants' overall experience with Marathon® and CavilonTM. Results from the survey will be reported using the appropriate descriptive statistics for the distribution and scale of the data.

At Visit 1, participants will be asked the following question regarding the SBP on each arm:

1. Is the SBP comfortable? (Likert-like scale)

At Visit 3 and Visit 6, participants will be asked the following questions regarding the SBP on each arm:

Medline Industries, LP
An evaluation of the skin protection characteristics of two commercially available skin barrier protectants
MED-2022-DIV71-003
08-AUG-2022

Version 2.0 CONFIDENTIAL Page 24 of 28

- 1. Do you see the SBP on your skin? (Yes/No)
- 2. Did the SBP accumulate dirt or debris? (Yes/No)
- 3. Did the SBP adhere to clothing or any other material? (Yes/No)

Additionally, at Visits 3 and 6, participants will be asked the following questions regarding the SBP on each arm:

1. On which arm (left or right) is it easier to visually determine that the SBP is present?

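### The visibility question offers only left or right, and completing the survey, which is not defined item by item, is a condition for entering the Corneometer analysis

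*Combined protocol and SAP*

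**What the plan says.** Section 8.8.2 lists the survey items. At Visits 3 and 6 participants answer, for each arm, "Do you see the SBP on your skin? (Yes/No"), and then a comparative item: "On which arm (left or right) is it easier to visually determine that the SBP is present". The comparative item has no printed option for neither arm or for no difference, and no instruction to skip it.

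Section 2.2 describes both products as clear films. For Marathon the text reads "adhering to the contours of the skin to form a transparent flexible film"; for Cavilon it reads "The film is transparent and possesses good oxygen and moisture vapor permeability".

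Section 8.3 defines the analysis population, labelled ITT, as participants "who have complete data for all time points and have completed the survey for the secondary endpoint", and adds that "No per protocol, safety, or other analyses groups are planned". Section 8.2 states: "If a participant has incomplete data, the participant will be replaced". Under Section 5.3, participants are "screened and enrolled until a total of 42 participants with complete data are obtained".

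**The concern.** There are two separate issues.

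The first is the item itself. The survey is the only secondary endpoint, and Section 8.5 singles out the visibility questions as the main use of skin phototype. The per-arm question accepts No for both arms, yet the comparative question then asks that participant to name an arm. A participant who sees both films equally well has the same difficulty. Answers given without a real preference add noise to a head-to-head product comparison and make the products look more alike than they are.

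The second is the population rule. Survey completion governs entry to the only analysis set, so a secondary questionnaire helps decide who contributes to the primary Corneometer comparison. This applies to any incomplete survey. A blank visibility item could be one way to trigger it. In that case the participants leaving the set might tend to be those whose films had worn more, which would tie exclusion to the quantity being measured.

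**Working it through.** **Step 1. Which response patterns have a truthful answer (Section 8.8.2).**

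| Per-arm answers | Truthful answer as printed |
|---|---|
| Yes on one arm, No on the other | The arm with Yes |
| Yes on both, one clearer | The clearer arm |
| Yes on both, equally clear | None |
| No on both | None |

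**Step 2. Size of the dilution.** Let p be the true share preferring one product among participants with a real preference, and q the share of all participants who guess.

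Reported share = (1 − q) × p + q × 0.50

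The 0.50 comes from Section 6.2.2, which gives each product an equal chance of the dominant or non-dominant arm. A guess unrelated to product, even a habitual *right*, therefore falls on each product half the time on average. The documents give neither p nor q. I assume p = 0.80 and a range for q:

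- q = 0.30: 0.70 × 0.80 + 0.30 × 0.50 = 0.56 + 0.15 = 0.71
- q = 0.50: 0.50 × 0.80 + 0.50 × 0.50 = 0.40 + 0.25 = 0.65
- q = 0.70: 0.30 × 0.80 + 0.70 × 0.50 = 0.24 + 0.35 = 0.59

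**Step 3. What existing items can recover.** Participants answering No on both arms can be identified and tabulated apart. If every guesser were of that kind, the dilution could be removed in full. Participants answering Yes on both and seeing no difference cannot be told apart from those with a real preference, so their guesses stay in. Recovery is partial.

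**Step 4. Does the population rule cost power?** The planned number reproduces. The standardised effect in Section 8.1 is (17.5 − 15)/5.05 = 0.495. With a noncentral t calculation at one-sided α = 0.0125, n = 42 is the smallest number reaching 80% power (0.807). Section 8.1 does not state sidedness; a two-sided test would need 49. Because incomplete participants are replaced until 42 are complete, the analysed number stays at 42. If a share b were excluded for an incomplete survey, enrolment would be 42/(1 − b), rounded up: 43, 45, 47 or 53 for b = 2%, 5%, 10% or 20% (assumed values). The risk lies in who is analysed, not in how many.

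**Step 5. Does one blank item make a survey incomplete?** Section 8.3 requires a completed survey, and Sections 5.3 and 8.2 speak of complete and incomplete data; these favour a strict reading. Section 8.7 says missing data will be quantified, and Section 8.8 bases percentages on the non-missing sample size; these favour a lenient one. The Section 8.8 wording looks generic, since it also covers continuous variables, for which Section 8.3 already requires complete data. No section settles the question.

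**The case against.** The strongest reply is that the survey form is not among the documents. Section 6.1.2 says the case report forms and other study documents are supplied separately. In the other items the bracketed answer type follows the question mark, whereas *left or right* sits mid-sentence and may simply explain the word *arm*. The form may already offer a third answer. This stands as a limit on the conclusion: the defect is in the protocol text, and if the form differs, Section 8.8.2 should say so.

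Second, the item is descriptive, with no test specified in Section 8.8.2, and part of the dilution can be undone by cross-tabulation. Both are true and keep the point small. Neither helps participants who see both films equally.

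Third, a reader might infer that a participant who leaves this one item blank is removed from the primary analysis. The documents do not say so, because completion is not defined item by item.

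Fourth, a reader might infer that such blanks would remove exactly the participants who lost both films. That does not follow. The films are transparent when intact, so not seeing one is not the same as having lost it, and a participant who has lost both may guess and stay in. Nor does any section say that both films are expected to be gone by Visit 6; Section 2.2.2 describes Cavilon as long-lasting and highly durable. A link between visibility and wear is plausible, but its direction and size in the Corneometer comparison cannot be established from the documents.

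**Conclusion.** Two things hold on the text. As printed, the comparative visibility item has no truthful answer for a participant who sees neither film or sees both equally. And survey completion is a condition for the only analysis population, so an incomplete survey can remove and replace a participant with full Corneometer data.

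The dilution figures (71:29, 65:35 and 59:41 in place of 80:20) are illustrations. They rest on an assumed true preference, on assumed guessing rates, and on guesses unrelated to product. No size can be given for any effect on the primary comparison, because the documents give no rate of blank answers and do not say how a blank item is treated. That part is conditional: a blank visibility item matters for the primary analysis only if it counts as an incomplete survey.

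This is a desirable improvement, not a flaw that undermines the trial.

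**What to change.** In Section 8.8.2 and on the survey form, add *no difference* and *not visible on either arm* as answers, or skip the item after No on both arms while still offering *no difference*. Report every answer level by product, including the number who skipped.

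In Section 8.3, delete survey completion as a condition for the Corneometer analysis. If it is kept at all, apply it only to the survey summaries and state whether one unanswered item makes a survey incomplete. Align the complete-data and replacement wording in Sections 5.3 and 8.2, so that an incomplete survey alone does not lead to replacement for the primary endpoint.

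The cost is two answer boxes and a few edited clauses. There will be fewer definite left or right preferences to report, and the number analysed may differ between the primary endpoint and the survey, so each table should show its own denominator.

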#### 9. SUPPORTING DOCUMENTATION AND OPERATIONAL CONSIDERATIONS

## 9.1. Regulatory and Ethical Considerations

# 9.1.1. Confidentiality and Privacy

Participant confidentiality and privacy is strictly held in trust by Medline. Therefore, the study protocol, documentation, data, and all other information generated will be held in strict confidence. No information concerning the study or the data will be released to any unauthorized third party. All study data will be identified with an anonymous participant ID number, and all CRFs and other documents containing data will have the participant ID number and no identifiable information. One master list linking participant ID numbers to participant name and other contact information will be maintained in a secure electronic database by the study personnel in the event identification of a participant is necessary (eg, due to an ADE). This is the only documentation that will link participant name and participant ID number.

Study personnel will ensure all documents for data collection are completed in accordance with GDP in order to ensure accurate interpretation of data. Data will be transferred from paper CRFs to a secure electronic database and analyzed with SAS® 9.4, which will allow for quality checks to identify data that appear inconsistent, incomplete, or inaccurate.

All study records will be maintained for a minimum of two years following study closeout; records will be maintained for a longer period of time as required by IRB or other regulations.

### 9.1.2. Safety Oversight

Safety oversight will consist of monitoring of visit activity, ADEs and SADEs by the PI, who is suitably qualified and experienced to evaluate any ADEs or SADEs. The PI will review all ADEs and SADEs and make any necessary safety determinations or visit activity modification that are in the best interest of the participant as necessary. See also Section 7.0 ADEs for reporting and management requirements.

# 9.1.3. Study Discontinuation

The study may be temporarily suspended or prematurely terminated if there is sufficient reasonable cause. Written notification, documenting the reason for study suspension or termination, will be Medline Industries, LP

An evaluation of the skin protection characteristics of two commercially available skin barrier protectants MED-2022-DIV71-003

08-AUG-2022

Version 2.0 CONFIDENTIAL Page 25 of 28

provided by the suspending or terminating party to the IRB. If the study is prematurely terminated or suspended, the PI or study personnel will promptly inform the IRB and will provide the reason(s) for the termination or suspension.

Circumstances that may warrant termination or suspension include, but are not limited to:

- Determination of unexpected, significant, or unacceptable risk to participants as determined by ADE review
- Insufficient compliance to protocol requirements
- Data that are not sufficiently complete and/or evaluable

Study may resume once concerns about safety, protocol compliance, and data quality are addressed, and satisfy the IRB.

# 9.1.4. Conflict of Interest Policy

The independence of this study from any actual or perceived influence is critical. Therefore, any actual conflict of interest of persons who have a role in the design, conduct, analysis, publication or any aspect of this trial will be disclosed and managed.

### 9.2. Protocol Deviations

It is the responsibility of the PI and study personnel to use continuous vigilance to identify and report deviations on a routine basis. All deviations must be addressed in study documents and reported to Medline. Protocol deviations must be sent to the reviewing IRB per their policies. The PI is responsible for knowing and adhering to the reviewing IRB requirements.

#### 9.3. Abbreviations

ADE	Adverse Device Event
CFR	Code of Federal Regulations
CRF	Case Report Form
CRO	Contract Research Organization
FDA	Food and Drug Administration
GCP	Good Clinical Practices
GDP	Good Documentation Practices
НСР	Healthcare Provider
HIPAA	Health Insurance Portability and Accountability Act

Medline Industries, LP

An evaluation of the skin protection characteristics of two commercially available skin barrier protectants MED-2022-DIV71-003

08-AUG-2022

Version 2.0 CONFIDENTIAL Page 26 of 28

HMDS	Hexamethyldisiloxane
ICF	Informed Consent Form
ICH	International Conference on Harmonisation
ID	Identification
IRB	Institutional Review Board
ITT	Intent to Treat
LP	Limited Partnership
MASD	Moisture-Associated Skin Damage
PI	Principal Investigator
PSF	Participant Screening Form
SAE	Serious Adverse Event
SADE	Serious Adverse Device Event
SBP	Skin Barrier Protectant
SOA	Schedule of Activities
UADE	Unanticipated Adverse Device Effect
US	United States

